**Table 4 Analysis Periods**

	Treatment Phase-1	Treatment Phase-2
Treatment Sequence A	3.0K + dialysate bath + SZC	2.0K + dialysate bath
Treatment Sequence B	2.0K + dialysate bath	3.0K + dialysate bath + SZC

Abbreviations: SZC = sodium zirconium cyclosilicate (Lokelma®)

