## Study design

This is a prospective, open-labelled, randomized, 2x2 cross-over design study of 88 patients with end stage renal disease (ESRD) receiving routine out-patient dialysis using a standard 2.0 potassium ion ( $K^+$ )/2.5 calcium ion ( $Ca^{++}$ ) dialysate bath. The overall aim of the study is to determine whether converting stable hemodialysis patients from a “standard” 2.0  $K^+$ /2.5  $Ca^{++}$  dialysate (without Lokelma) to a 3.0  $K^+$ /2.5  $Ca^{++}$  mEq dialysate supplemented with the orally administered potassium binder sodium zirconium cyclosilicate (Lokelma®) to treat interdialytic hyperkalemia will reduce the incidence and duration of post-dialysis atrial fibrillation.

Following screening, eligible subjects will undergo placement of an implantable cardiac loop recorder (LINQ device) to monitor for the development of atrial fibrillation or any clinically significant cardiac arrhythmias [CSCA]). After a two-week recovery period (to allow the patient to heal from cardiac loop recorder placement), patients will be randomized (1:1 ratio) to one of two treatment sequences:

- Sequence **A**: standard 2.0  $K^+$ /2.5  $Ca^{++}$  dialysate with no Lokelma supplementation for two (2) months, followed by a cross-over to experimental 3.0  $K^+$ /2.5  $Ca^{++}$  dialysate with Lokelma supplementation (on off-dialysis days) for two (2) months;

Or

- Sequence **B**: experimental 3.0  $K^+$ /2.5  $Ca^{++}$  dialysate with Lokelma supplementation (on off-dialysis days) for two (2) months, followed by standard 2.0  $K^+$ /2.5  $Ca^{++}$  dialysate with no Lokelma supplementation for two (2) months.

Each two-month treatment period (both 2.0  $K^+$ /2.5  $Ca^{++}$  dialysate and 3.0  $K^+$ /2.5  $Ca^{++}$  dialysate with Lokelma sequences) will be preceded by a two-week run-in period, to allow the patient to adapt to the new dialysate bath.

While receiving the higher  $K^+$  dialysate, patient will be treated on off-dialysis days (4 days/week) with Lokelma, titrated to maintain  $K^+$  between 4.0 and 5.5 mEq/L. Refer to section 7.2 for the initial dose and frequency details.

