### **3.5 Methods for Assigning Treatment Groups**

The study sponsor (NephroNet) will be responsible for preparing the randomization scheme. Permuted block randomization using 2x2 Latin Squares will be applied to ensure a balanced assignment (1:1 ratio) to the two treatment sequences in the study.

Patients who meet all inclusion and none of the exclusion criteria will be randomized to one of two treatment sequences, consistent with a two-period cross-over design:

- Sequence **A**: standard 2.0 K+/2.5 Ca++ dialysate with no Lokelma supplementation for two (2) months, followed by a cross-over to experimental 3.0 K+/2.5 Ca++ dialysate with Lokelma supplementation (on off-dialysis days) for two (2) months;

Or

- Sequence **B**: experimental 3.0 K+/2.5 Ca++ dialysate with Lokelma supplementation (on off-dialysis days) for two (2) months, followed by standard 2.0 K+/2.5 Ca++ dialysate with no Lokelma supplementation for two (2) months.

Central randomization via an interactive response technology (IRT) will be utilized. Randomization codes will be assigned strictly sequentially as patients become eligible for randomization. Randomization will occur by the site PI (or qualified designee) contacting the IRT and obtaining the randomization code and associated treatment sequence for each eligible patient. The original randomization notification will be filed as part of the source documents.

Sites are expected to randomize approximately nine (9) patients on average (no minimum or maximum number of enrolled patients will be specified).

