### **8.2 Sample Size Estimate**

The primary statistical hypothesis of the study is that the rate of atrial fibrillation events during hemodialysis using the 3.0 K+ dialysate bath supplemented with sodium zirconium cyclosilicate (Lokelma®) is not equal to the rate of events incurred during hemodialysis using the 2.0 K+ dialysate bath.

The sample size estimation is based upon the primary statistical hypothesis, and its details were separately documented.

With >90% power to reject the primary hypothesis, 40 subjects would need to be randomized into one of two treatment sequences in the 2x2 cross-over study using the simulation study with a 2-sided alpha of 0.05, assuming an event rate of 4.6 with the 2.0 K+ dialysate bath, an overdispersion parameter of 0.07 and a reduction of rate ratio of 25%. It is expected that 10% of randomized subjects will not complete both study periods. Accounting for this estimated 10%

attrition rate, **44 subjects** per treatment sequence or **88 subjects** in total will be randomized in the study.

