#### **8.3.3 Safety Analysis Set**

The Safety Analysis Set will include all randomized participants who during the first treatment period (study Phase I): (i) received at least one dose of the study drug (Lokelma) during treatment with the 3.0 K+ dialysate bath; or (ii) completed Visit 2 during treatment with the 2.0 K+ dialysate bath. All safety endpoints will be analyzed using the SAS.

The number of participants in each analysis set, and the number excluded and associated reasons will be summarized by treatment group and overall. In addition, the following periods will be defined for the purpose of reporting:

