### **8.4 Outcome Measures for Analyses**

#### **8.4.1 Primary Efficacy Endpoint: Frequency of Atrial Fibrillation Events**

The primary efficacy endpoint is the frequency of atrial fibrillation events occurring during the 8-week Treatment Phase-1 and the 8-week Treatment Phase-2 dialysate cross-over periods. Atrial fibrillation will be defined as irregular heart rhythms and irregular R-R intervals in the absence of definable P waves for a minimum of 6 minutes. Each atrial fibrillation event will be adjudicated and validated as a true atrial fibrillation event by a central cardiologist who is blinded to dialysate K+ content.

The total number of atrial fibrillation events will be compared between the two dialysate groups.

The primary objective of the study will have been achieved if the frequency of atrial fibrillation events occurring during experimental treatment (hemodialysis using 3.0K+/2.5 Ca++ dialysate bath, with Lokelma supplementation on off-treatment days) is lower compared to standard treatment (hemodialysis using 2.0K+/2.5 Ca++ dialysate bath, without Lokelma supplementation).

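### Table 4 defines Sequences A and B the opposite way round from the synopsis and Sections 1.4 and 3.5; decoding Section 3.5 codes with it would invert the primary rate ratio

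*Protocol*

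**What the plan says.** Section 3.5, which governs assignment, defines the first sequence as "Sequence A: standard 2.0 K + /2.5 Ca ++ dialysate with no Lokelma supplementation for two (2) months, followed by a cross-over to experimental" treatment with 3.0 K+ dialysate and Lokelma; Sequence B is the reverse. The study design part of the synopsis and Section 1.4 define both sequences in the same way. Section 3.5 also says that the site contacts the IRT, "obtaining the randomization code and associated treatment sequence for each eligible patient".

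Section 8.3.3 closes by announcing that "the following periods will be defined for the purpose of reporting", and Table 4 follows. Its first row is "Treatment Sequence A 3.0K + dialysate bath + SZC 2.0K + dialysate bath", under the headings Treatment Phase-1 and Treatment Phase-2. Its second row, for Sequence B, has 2.0 K+ in Phase-1 and 3.0 K+ with SZC in Phase-2.

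Section 8.3.2 analyses efficacy by randomized allocation rather than by treatment received. Section 8.4.1 makes success directional: "The primary objective of the study will have been achieved if the frequency of atrial fibrillation events occurring during experimental treatment" is lower than on standard treatment.

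**The concern.** The two definitions of A and B exclude each other. All are current text, and each row of Table 4 is complete and coherent, so this does not look like a damaged table. It is also not a detail left to the SAP, because the protocol states the mapping itself and does so in two opposite ways.

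Table 4 stands in the statistical section, and Section 8.1 says that the SAP will describe the analyses of that section in more technical detail. A SAP author or programmer who has a sequence code and a phase, and who has to assign treatment by randomization, could reasonably look there. If the codes were issued under Section 3.5, that lookup would exchange the two treatments in every patient. A two-sided test gives no warning of this, and the success rule depends on the sign. A true benefit would be reported as harm, or a true harm as success.

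**Working it through.** **1. The definitions side by side**

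| Source | A, Phase 1 | A, Phase 2 | B, Phase 1 | B, Phase 2 |
|---|---|---|---|---|
| Synopsis, Section 1.4, Section 3.5 | 2.0 K+, no Lokelma | 3.0 K+ with Lokelma | 3.0 K+ with Lokelma | 2.0 K+, no Lokelma |
| Table 4 | 3.0 K+ with SZC | 2.0 K+ | 2.0 K+ | 3.0 K+ with SZC |

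Four of four cells disagree.

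**2. Inputs (Section 8.2)**

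- Event rate 4.6 on 2.0 K+. No time unit is given; I assume one 8-week period.
- 25% reduction, so the rate on 3.0 K+ is 4.6 × 0.75 = 3.45.
- Overdispersion k = 0.07, two-sided alpha 0.05.
- 40 subjects, read as 40 per sequence (80 in total), because the plan goes on to 44 per sequence and 88 in total. The allowance is "It is expected that 10% of randomized subjects will not complete both study periods".
- The correlation between a patient's two periods is not stated, so both extremes are shown: overdispersion independent between periods, or fully shared within the patient.

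**3. The plan's own figure**

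- Independent: SE(log RR) = √[(1/4.6 + 1/3.45 + 2 × 0.07)/80] = 0.0899. |ln 0.75| = 0.2877, so z = 3.20 and power = Φ(3.20 − 1.96) = 89.2%.
- Shared: SE = √[(1/4.6 + 1/3.45)/80] = 0.0796, z = 3.61, power = 95.1%.
- Simulation of the cross-over (300 trials per setting; negative binomial model with treatment and period terms, independence working correlation, robust Wald test) gave 90.3% and 96.3%.

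The stated power of more than 90% is reproduced to within about a point at the lower extreme. Reading 40 as the total would give only 62% to 72%.

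**4. Effect of exchanging the labels**

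The primary model has terms for treatment and period. With treatment indicator t, a full exchange replaces t by 1 − t. The treatment coefficient β becomes −β, the intercept absorbs β, and the period term and the standard error do not change. So RR becomes 1/RR, the confidence limits become reciprocals, and the two-sided p-value is the same.

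At the planning figures with 80 completers, expected events are 80 × 4.6 = 368 on 2.0 K+ and 80 × 3.45 = 276 on 3.0 K+.

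| Correlation assumption | Correct labels: RR (95% CI) | Exchanged labels: RR (95% CI) | p, both |
|---|---|---|---|
| Independent | 0.75 (0.63 to 0.89) | 1.33 (1.12 to 1.59) | 0.0014 |
| Shared | 0.75 (0.64 to 0.88) | 1.33 (1.14 to 1.56) | 0.0003 |

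One simulated data set, fitted both ways, gave RR 0.782 (0.682 to 0.896) and 1.279 (1.116 to 1.466), with p = 0.0004 each time.

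**5. Number of labels affected**

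80 completers × 2 periods = 160 patient-periods. The upper bound is 88 × 2 = 176.

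**The case against.** The strongest reply is that the letter A or B enters no analysis the protocol specifies. The primary model has treatment and period terms and no sequence term. The success rule, the secondary endpoints, entry to the Safety Analysis Set, the windows for treatment-emergent events and the cross-over instructions in Section 4.2.3 are all written in terms of dialysate and Lokelma. Table 4 is introduced for reporting, so the likelier damage is mislabelled tables. The trial is open label, packets are counted weekly, and Section 7.5 has drug administration entered in the eCRF. A full exchange would show Lokelma dispensed throughout the supposed 2.0 K+ periods and none in the others, which someone should notice. Three concordant places also make the intended reading fairly clear.

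Much of this stands. The inversion is a risk and not a certainty, and it needs Section 3.5 codes to be decoded with Table 4. No exchange of safety results should be claimed, because Safety Set entry and the adverse-event windows rest on what the patient received (Sections 8.3.3 and 8.5.6). The fault is an inconsistency of labels rather than a deliberate analysis choice. The confidence intervals and p-values above only illustrate the effect.

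It does not remove the point. Section 8.3.2 requires efficacy to be analysed by randomized allocation, which makes deriving treatment from the sequence code more plausible. The protocol does not show which definition the IRT list follows. A cross-check against dispensing data would catch the error only if someone ran it, and neither the p-value nor the power would prompt that.

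**Conclusion.** The concern holds. Table 4 contradicts the synopsis, Section 1.4 and Section 3.5 in every cell, and nothing in the protocol resolves it. If Section 3.5 codes are decoded with Table 4, the primary rate ratio is replaced by its reciprocal, 0.75 becoming 1.33 at the planned effect, with an unchanged p-value and a reversed conclusion. That result follows from the model's form and does not depend on the event rate, its time unit or the within-patient correlation; only the illustrative intervals and p-values do. No inversion occurs if treatment by period comes from recorded dialysate and Lokelma data, or if the IRT list uses Table 4's labels. Other by-treatment comparisons are affected only if they are built from the same mapping. Correction is warranted before the SAP or any programming relies on Table 4, because the worst case reverses the trial's main finding.

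**What to change.** Check which definition of Sequences A and B the IRT randomization list uses. Make the synopsis, Section 1.4, Section 3.5 and Table 4 agree with it. With three places against one, the expected correction is to swap the two rows of Table 4 so that they match Section 3.5. Carry the agreed mapping into the SAP and the programming specifications.

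The cost is one check against the list and a two-row table correction. Design, sample size, power and data collection do not change.

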### **8.4 Outcome Measures for Analyses**

#### **8.4.1 Primary Efficacy Endpoint: Frequency of Atrial Fibrillation Events**

The primary efficacy endpoint is the frequency of atrial fibrillation events occurring during the 8-week Treatment Phase-1 and the 8-week Treatment Phase-2 dialysate cross-over periods. Atrial fibrillation will be defined as irregular heart rhythms and irregular R-R intervals in the absence of definable P waves for a minimum of 6 minutes. Each atrial fibrillation event will be adjudicated and validated as a true atrial fibrillation event by a central cardiologist who is blinded to dialysate K+ content.

The total number of atrial fibrillation events will be compared between the two dialysate groups.

The primary objective of the study will have been achieved if the frequency of atrial fibrillation events occurring during experimental treatment (hemodialysis using 3.0K+/2.5 Ca++ dialysate bath, with Lokelma supplementation on off-treatment days) is lower compared to standard treatment (hemodialysis using 2.0K+/2.5 Ca++ dialysate bath, without Lokelma supplementation).

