#### **8.4.2 Secondary Efficacy Endpoint #1: Frequency and duration of Clinically Significant Cardiac Arrhythmia Events**

Frequency and duration of CSCAs (bradycardia, ventricular tachycardia and/or asystole) events during the 8-week Phase-I dialysate cross-over period and the 8-week Phase-II cross-over period is a secondary efficacy endpoint. Definitions of CSCA events are provided in [Section 5.1.2](#).

This secondary objective will have been achieved if the frequency of post-dialysis CSCAs event (bradycardia, ventricular tachycardia and/or asystole) is lower during experimental compared to standard treatment or if a total duration of post-dialysis CSCAs event (bradycardia, ventricular tachycardia and/or asystole) is shorter during experimental compared to standard treatment.

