#### **8.5.1 General Considerations**

Inference concerning the primary analysis will be performed at the 2-sided 5% significance level. All point estimates will be presented together with confidence intervals of 2-sided 95% coverage.

The analysis assumes that there is no carry-over effect given that the wash-out period is deemed appropriate to rule out this effect by design.

Intercurrent events are handled as outlined within each section for the primary and secondary endpoint analyses below. For the primary endpoint and secondary endpoints, missing data will occur in the case where participants are lost to follow-up, provide insufficient evaluable data, withdraw consent, or die during the study. The proportion of participant missing data will be presented as appropriate.

For each participant, baseline is defined as the last available assessment prior to or on the date of the randomization visit, unless otherwise specified. A period baseline is defined as the last available assessment prior to or on the date of each of periods

In general terms, the Full Analysis Set (FAS) will be used for the efficacy analyses and the Safety Analysis Set will be used for the safety analyses.

In general, all baseline characteristics and efficacy and safety variables will be summarized using descriptive statistics as appropriate. Continuous variables will be summarized by descriptive statistics including number of participants (n), mean, standard deviation, minimum, median, and maximum. Categorical variables will be summarized using frequencies and percentages, where the denominator of the calculation is the underlying analysis set population unless otherwise stated.

Descriptive statistics of quantitative efficacy and safety parameters by scheduled visits will be provided on observed cases (i.e., including only participants who have non-missing assessments at a given visit).

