### **8.5.2 Analysis of the Primary Variable**

The primary efficacy endpoint is the frequency of atrial fibrillation events occurring during the 8-week Treatment Phase-1 and the 8-week Treatment Phase-2 dialysate cross-over periods.

The primary analysis will test the null hypothesis that there is no difference in the rate of atrial fibrillation events between the 3.0K+ dialysate bath with Lokelma and the 2.0K+ dialysate bath without Lokelma, against the alternative hypothesis that there is a difference in the rate of atrial fibrillation events between the 3.0K+ dialysate bath with Lokelma and the 2.0K+ dialysate bath without Lokelma. Statistical hypothesis testing will be completed at a 2-sided 0.05 significance level.

The primary analysis will not account for missing values. However, sensitivity analyses will be conducted using the pattern mixture model with multiple imputation (PM-MI) method. Details of the PM-MI method will be provided in the SAP.

A generalized linear model assuming the distribution of negative binomial will be used, with fixed effect terms for the treatment groups (3.0K+ dialysate bath with Lokelma and 2.0K+ dialysate bath without Lokelma), the study period, and log (the duration of period) as an offset variable. An unstructured working variance-covariance will be employed. Additional model terms may be included, details of which will be described in the SAP. The estimated risk ratio between groups and its 95% robust confidence interval (CI) will be displayed. The null hypothesis will be rejected if the p-value (based upon the Wald statistics) is less than 0.05.

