### **8.5.3 Analysis of the Secondary Variables**

Each secondary endpoint will be analyzed individually, and no multiplicity control will be applied. Analyses of secondary variables will not account for missing values.

The secondary endpoint of clinically significant arrhythmia events will be analyzed similarly to the primary endpoint.

The secondary endpoint of a total duration of clinically significant arrhythmia events will be analyzed by a linear mixed model. Details of the model specifications will be in the SAP

The secondary endpoint of risk of outside K+ safe range will be analyzed with a similar approach of the primary endpoint but with a logit link function. Details of the model specification will be included in the SAP.

A nominal p-value and a 95% C.I. of the effect between two treatment groups will be reported for each of secondary endpoints.

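### Section 8.4.2 declares a secondary objective achieved on direction alone, for either of two measures; Section 8.4.1 does not join its directional success sentence to the test in Section 8.5.2

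*Protocol*

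**What the plan says.** Only two places in the protocol state when an efficacy objective counts as achieved.

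- **Section 8.4.1 (primary).** "The primary objective of the study will have been achieved if the frequency of atrial fibrillation events occurring during experimental treatment", defined there as the 3.0 K+ bath with Lokelma, "is lower compared to standard treatment". The section names no test, p-value or interval and does not point to Section 8.5.2.
- **Section 8.4.2 (secondary #1).** "This secondary objective will have been achieved if the frequency of post-dialysis CSCAs event" is lower on experimental treatment, "or if a total duration of post-dialysis CSCAs event" is shorter. Again no test is named, and either limb is enough.

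The inferential rules stand elsewhere.

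- **Section 8.5.1.** "Inference concerning the primary analysis will be performed at the 2-sided 5% significance level". The sentence covers the primary analysis only.
- **Section 8.5.2.** The alternative hypothesis is a difference in either direction. "Statistical hypothesis testing will be completed at a 2-sided 0.05 significance level", and "The null hypothesis will be rejected if the p-value (based upon the Wald statistics) is less than 0.05". The section does not mention achievement of the objective.
- **Section 8.5.3.** Secondary endpoints are analysed one by one, "no multiplicity control will be applied", and each gets a nominal p-value and a 95% confidence interval. No threshold is set for calling a secondary objective met.

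Section 8.4.3 (potassium range) states an aim but no achievement rule.

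**The concern.** A success sentence should say what evidence is needed. The one in 8.4.2 asks only for a direction and offers two chances to get it. Nothing in 8.5.3 adds a threshold, so this either/or sentence is the only criterion the protocol gives for that objective. A report that followed it could state that the CSCA objective was met on a chance difference in one measure, even if the other measure went the wrong way.

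For the primary endpoint the two halves of a proper rule exist but are kept apart: 8.4.1 has a direction without a test, and 8.5.2 has a test without a direction. Rejection under 8.5.2 alone could also mean more atrial fibrillation on experimental treatment.

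This is not detail left to the statistical analysis plan. The protocol states the achievement rules itself, and it is these stated rules that need correcting.

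**Working it through.** **Inputs from the protocol**

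- Primary test: two-sided 0.05 Wald test (8.5.1, 8.5.2).
- Sample size (8.2): 40 subjects per sequence, control rate 4.6, overdispersion 0.07, 25% reduction, power above 90%.
- CSCA rule: frequency lower or duration shorter (8.4.2); no threshold and no multiplicity control (8.5.3).

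**Assumptions**

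- The rate of 4.6 is per 8-week period. The protocol gives no unit. Read per 6 months or per year, power at 80 subjects would be about 49% or 28%, so only the per-period reading fits the stated power.
- The correlation ρ between the estimated effects on CSCA frequency and duration is not given. The range 0 to 1 is shown.
- Under no effect both CSCA estimates are treated as bivariate normal about zero.

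**Step 1. Reproduce the stated power (80 subjects, rates 4.6 and 4.6 × 0.75 = 3.45)**

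- Overdispersion independent between periods: SE² = (1/4.6 + 1/3.45 + 2 × 0.07)/80 = 0.6472/80, so SE = 0.0899. Power = Φ(0.2877/0.0899 − 1.96) = 89.2% (simulated 89.4%).
- Overdispersion shared within a subject: SE² = (1/4.6 + 1/3.45)/80 = 0.5072/80, so SE = 0.0796. Power = Φ(0.2877/0.0796 − 1.96) = 95.1% (simulated 94.4%).

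The stated figure of above 90% is reproduced to within about a point. The design was therefore sized for the two-sided 0.05 test, not for a bare comparison of frequencies.

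**Step 2. Primary endpoint under no effect (simulated, 40 per sequence)**

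| Rule | Chance of being met |
|---|---|
| 8.4.1 sentence alone: experimental total lower | 49.4% to 49.9% (ties 1.4% to 1.8%, counted as not met) |
| 8.5.2 alone: any rejection | 5.1% to 5.6% |
| 8.5.2 rejection and lower rate on experimental treatment | 2.3% to 3.0% (nominal 2.5%) |

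These use the protocol's overdispersion of 0.07. With a far larger value of 3, the last row was 3.7%.

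**Step 3. CSCA rule under no effect, as written**

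P(at least one measure favourable) = 1 − [1/4 + arcsin(ρ)/(2π)].

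- ρ = 0: 1 − 0.25 = 75.0%
- ρ = 0.5: 1 − (0.25 + 0.0833) = 66.7%
- ρ = 0.8: 1 − (0.25 + 0.1476) = 60.2%
- ρ = 0.9: 1 − (0.25 + 0.1782) = 57.2%
- ρ = 1: 1 − 0.5 = 50.0%

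**Step 4. CSCA rule with a nominal two-sided 0.05 test, favourable direction, on either measure**

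P = 0.025 + 0.025 − P(both significant and favourable). At ρ = 0 this is 0.05 − 0.025² = 4.9%. It is 4.5% at ρ = 0.5, 3.9% at ρ = 0.8 and 2.5% at ρ = 1. Adding a test removes nearly all of the problem; what remains is the either/or.

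**The case against.** The strongest reply concerns the primary endpoint. Section 8.4 lists outcome measures and Section 8.5 holds the decision rules. Section 8.5.1 fixes the two-sided 5% level, 8.5.2 rejects only if p is below 0.05, and the sample size rests on the same test. Taken as a whole, concluding that the frequency is lower is an inference governed by 8.5, and the direction in 8.4.1 supplies what the two-sided test lacks. This stands. A reader might infer from 8.4.1 alone that the trial has a 50% chance of false success on its primary endpoint. The documents do not support that: 8.4.1 does not say that an observed difference suffices, and the test level is fixed elsewhere. What remains is a missing link.

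A second reply is that the 75% figure is an extreme. This also stands. It is the zero-correlation limit, applies only to the CSCA rule and never to the primary endpoint. Frequency and total duration are built from the same events, so a positive correlation and a lower figure are more plausible. Even at full correlation, however, the rule as written is met half the time by chance.

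A third reply is that 8.5.3 openly treats secondary endpoints as nominal, so a testing hierarchy would be the reviewer's preference. That is fair, and no hierarchy is required here. But a nominal endpoint sits badly with a sentence that declares its objective achieved.

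The success sentence in 8.4.2 also speaks of post-dialysis CSCAs, while the endpoint covers the whole 8-week periods. The same mismatch appears in the objectives (Synopsis, Section 2.2) and in Section 5.1.2. It is a separate question of which events count and plays no part in the figures above.

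**Conclusion.** The point holds for 8.4.2 and, in a weaker form, for 8.4.1.

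- **Secondary #1.** The stated rule has no significance criterion anywhere in the protocol and is met by either of two measures. Under no effect it is met about 50% to 75% of the time, about 60% at a correlation of 0.8. The correlation is an assumption; the lower bound of 50% holds for any correlation between 0 and 1.
- **Primary.** The directional success sentence and the non-directional test are never joined. Read together they give about 2.5% error in the favourable direction, given the protocol's overdispersion. Because 8.5.1 and 8.5.2 already set the test level, this is a wording defect and not a loss of error control.

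**What to change.** - **Section 8.4.1.** Replace the success sentence with: *achieved if the two-sided p-value in Section 8.5.2 is below 0.05 and the estimated rate ratio (3.0 K+ with Lokelma vs 2.0 K+) is below 1*.
- **Section 8.4.2.** Delete the success sentence and report CSCA frequency and total duration as nominal estimates with 95% confidence intervals, which matches 8.5.3. If the sponsor wants to keep a success claim, tie it to a stated significance criterion that accounts for the two measures, for example by testing them in a fixed order or requiring both.

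The cost is two sentences of protocol wording. Design, sample size, data collection and the planned models do not change.
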